## 7 Statistical analysis

### 7.1 Sample size

The sample size has been calculated using the on-line tool GRANMO v7.12 (<https://www.imim.es/ofertadeserveis/software-public/granmo>). Data obtained in the previous pilot trial regarding total sperm count per ejaculate were used as a reference. With the aim to determine differences between the mean of the two experimental groups, and accepting an alpha risk of 0.01 and a beta risk of 0.2 in a two sided test, a total of 46 individuals per group are necessary to recognize as statistically significant a difference greater than or equal to  $20 \times 10^6$  spermatozoa/ml of ejaculate. The common standard deviation is assumed to be 25 (the maximum value in the previous pilot trial), with an anticipated drop-out rate of 20%. In that way, a total of 100 subjects, 50 per experimental group, will be recruited for the present clinical trial.

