### 4 Study Design

Monocentric, prospective, randomized, double-blind and placebo-controlled clinical study to evaluate clinical parameters, seminal quality, oxidative stress and DNA fragmentation, in astheno/oligozoospermic patients attending to the Andrology unit of the “Hospital Clínic de Barcelona”.

They will be randomized into two groups: experimental group (TSOD food supplement) and control group (Placebo). The experimental group will receive a daily dose of 250 mg of TetraSOD® during three months and the control group will receive a daily dose of placebo during the same period of time. After three months of treatment, both groups will stop using TetraSOD® or placebo and a wash-out period of 3 months will start.

The intervention group will be assigned to each patient according to the assigned code in order of inclusion to the study and that will serve for the randomization of the patients. The code lists will be previously prepared through an informatic program. The ratio of experimental and control group will be 1:1. The randomization numbers will be distributed by blocks. The study is designed to make the assignment double-blind; therefore, the randomization sequence will be hidden and only visible by the study monitor.

The Placebo and TetraSOD® capsules will be prepared in such a way that they are indistinguishable from each other. The participants in the study, as well as the technicians in contact with the patients, in charge of preparing questionnaires, distributing capsules, taking samples, etc., will not be able to know which capsules correspond to each experimental group.

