### 7.2 Statistical analysis

A descriptive statistic of all the variables collected will be made.

The categorical variables will be presented in the form of lists of frequencies and proportions. For the quantitative variables, central tendency (mean and median) and dispersion (standard deviation, maximum and minimum values) will also be presented.

A double-blind randomized placebo-controlled clinical study to verify the efficacy of TetraSOD® in the improvement of semen quality in patients with idiopathic infertility.

Initial demographic and anthropometric characteristics of patients in TetraSOD® and placebo groups will be compared with independent t-test for continuous variables and chi square test for categorical ones. The non-parametric Mann-Whitney test will be applied to evaluate the effects of the dietary supplementation with TetraSOD® group vs. placebo group at the same time of study (time 0, 90 d or 180 d). Within each experimental group (TetraSOD® and placebo), the non-parametric Friedman test for matched-pairs will be applied in order to determine statistically significant differences of data recorded at the three sampling times (0, 90 d and 180 d). Significance will be accepted for  $p < 0.05$ . All analyses will be conducted with Prism 6 software.

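### Section 7.1 sizes the between-group comparison at two-sided alpha 0.01, but section 7.2 tests everything at 0.05, and nothing links the two levels

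*Combined protocol and SAP*

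**What the plan says.** Section 7.1 (Sample size) describes a comparison of two group means, "accepting an alpha risk of 0.01 and a beta risk of 0.2 in a two sided test". The target difference is 20 million spermatozoa per ml. For the spread, "The common standard deviation is assumed to be 25", and the calculation is made "with an anticipated drop-out rate of 20" percent. The result is 46 per group, and the recruitment target is set at 50 per group, 100 in total. Section 4 (Study Design) adds that "The ratio of experimental and control group will be 1:1".

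Section 7.2 (Statistical analysis) specifies Mann-Whitney tests between arms at 0, 90 and 180 days and Friedman tests within each arm. It then gives a single rule for all of them: "Significance will be accepted for" p<0.05.

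Neither section mentions the other's level. The plan gives no reason for 0.01, does not say which tests it covers, and describes no multiplicity adjustment.

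**The concern.** A sample size calculation states the error risks of the test that will decide the question. Here the level used for sizing and the level used for analysis differ by a factor of five, so the alpha and power in 7.1 do not belong to the test in 7.2. A between-group p-value from 0.01 up to 0.05 on sperm count would be significant under 7.2, yet would miss the level at which 7.1 says the target difference is to be recognised.

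This matters more because the plan has no other control on false positives. The main variable in section 3.3 is the whole set of WHO seminal parameters, with no single primary variable, and 7.2 tests at several times and also within arms. The 0.01 in 7.1 is the only stricter level in the plan.

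**Working it through.** **Inputs.** From 7.1: two-sided alpha 0.01, beta 0.2, difference 20, SD 25, drop-out 20%. From section 4: 1:1 allocation. From 7.2: threshold 0.05. The SD is given without a unit; I assume it has the same unit as the difference.

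**Reproducing the plan's figure.** For two means, by normal approximation, evaluable n per group = 2 × (z for alpha + z for power)² × (SD/difference)². Here 2 × (25/20)² = 3.125. For drop-out, divide by 1 − 0.20 = 0.80.

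| Level | z for alpha + z for power | Evaluable per group | After drop-out |
|---|---|---|---|
| 0.01 two-sided | 2.576 + 0.842 | 36.5 | 45.6 |
| 0.05 two-sided | 1.960 + 0.842 | 24.5 | 30.7 |
| 0.01 one-sided | 2.326 + 0.842 | 31.4 | 39.2 |
| 0.05 one-sided | 1.645 + 0.842 | 19.3 | 24.2 |

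Only two-sided 0.01 gives the stated 46. Rounding up to whole patients before the drop-out step gives 47 at 0.01 and 32 at 0.05, which does not change the conclusion. So 0.01 is the level actually used.

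**Error rate.** At p<0.05 the nominal false-positive rate of one comparison is 0.05 against 0.01, and 0.05/0.01 = 5. This ratio is per comparison.

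**Power and detectable difference.** With 50 recruited and 20% lost, 50 × 0.80 = 40 are evaluable per arm, and the standardised difference is 20/25 = 0.8.

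| Quantity, 40 per arm | At 0.01 | At 0.05 |
|---|---|---|
| Power, t-test (non-central t) | 82% | 94% |
| Power, Mann-Whitney (simulated, normal data) | about 80% | about 93% |
| Difference with 80% power, t-test | 19.5 | 15.9 |
| Smallest observed difference reaching significance, t-test | 14.8 | 11.1 |

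The last row assumes an observed SD of 25. Observed mean differences between about 11 and 15 would then be significant under 7.2 but not at the level used in 7.1.

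**The case against.** The strongest reply is that 7.1 is a planning calculation, while 7.2 contains the only explicit analysis threshold. On that view 0.05 simply governs. The sized comparison then has a conventional 5% two-sided error rate and more than 90% power, and the trial is larger than its test requires, which does no harm to power. Much of this stands. It does not make 7.1 correct: if 0.05 governs, 7.1 misstates both the alpha accepted and the power obtained.

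Four stronger readings are tempting, and the documents do not support them.

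- *A reader might infer that the trial is underpowered.* It is not. Testing at 0.05 a sample sized at 0.01 raises power.
- *A reader might infer that the trial as a whole carries five times its intended error.* No trial-wide error rate is defined, so the factor applies only to each comparison.
- *A reader might take 0.01 as a Bonferroni allowance of 0.05/5 that the analysis then discards.* The division is exact, but the plan gives neither a count of five tests nor any multiplicity reason for 0.01.
- *A reader might infer that the sponsor is free to choose the level after seeing the data.* Section 7.1 contains no separate success rule, and moving from 7.2 to 0.01 would only tighten the bar. The wider freedom lies in the open set of main variables.

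**Conclusion.** The inconsistency is real and should be corrected. The comparison sized at a two-sided 1% level will be tested at a nominal 5%, and the 80% power in 7.1 is not the power of the planned test. The effect is a looser evidence standard than the one used for sizing, with no loss of power. Nothing in 7.1 is miscalculated, since 46 per group reproduces.

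The mismatch in alpha rests on the text alone. The power figures also assume SD 25 in the units of the difference, 40 evaluable per arm and normal data. The Mann-Whitney figures come from simulation and would change under another distribution.

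**What to change.** Before unblinding, state one two-sided alpha for the sized between-arm comparison at 90 days and use it in both sections. The documents do not favour either level, so the sponsor should choose and give the reason.

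- **(a) Use 0.01.** State in 7.2 that this comparison is positive only at two-sided p<0.01. Keep 0.05 for the other tests and label them secondary. The cost is a stricter threshold for the headline claim.
- **(b) Use 0.05.** Restate 7.1 at 0.05. With 40 evaluable per arm, a difference of 20 and SD 25, power is about 94% by t-test and about 93% by Mann-Whitney under normality; the t-test has 80% power for a difference of about 16. The cost is a less strict stated alpha.

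Under either option the level must be tied to one named sperm-count variable with consistent units. Section 7.1 takes total count per ejaculate as its reference but expresses the difference per ml, and no section names a single primary test; section 3.1 points only to 3 months. The change is therefore a few sentences across 7.1 and 7.2. It needs no extra patients.

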### 7.2 Statistical analysis

A descriptive statistic of all the variables collected will be made.

The categorical variables will be presented in the form of lists of frequencies and proportions. For the quantitative variables, central tendency (mean and median) and dispersion (standard deviation, maximum and minimum values) will also be presented.

A double-blind randomized placebo-controlled clinical study to verify the efficacy of TetraSOD® in the improvement of semen quality in patients with idiopathic infertility.

Initial demographic and anthropometric characteristics of patients in TetraSOD® and placebo groups will be compared with independent t-test for continuous variables and chi square test for categorical ones. The non-parametric Mann-Whitney test will be applied to evaluate the effects of the dietary supplementation with TetraSOD® group vs. placebo group at the same time of study (time 0, 90 d or 180 d). Within each experimental group (TetraSOD® and placebo), the non-parametric Friedman test for matched-pairs will be applied in order to determine statistically significant differences of data recorded at the three sampling times (0, 90 d and 180 d). Significance will be accepted for  $p < 0.05$ . All analyses will be conducted with Prism 6 software.

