### 5.1 Inclusion criteria

- Age: 18 to 45
- Male patients with idiopathic infertility classified with asthenozoospermia, oligozoospermia or oligoasthenozoospermia after seminal assessment.
- Not achieving pregnancy after at least one year of intercourse with the same partner without protective measures

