## 6.2 3 months Visit (V3months)

During this visit semen samples will be collected as was done at V0. The following analyses will be performed:

- Semen analysis as described in the manual of the WHO 2010 (15)
- Sperm DNA fragmentation
- SORP
- Sperm ROS intracellular and sperm DNA oxidation
- Blood analytics, to determine hormones (testosterone, Prolactin, FSH, LH, inhibin)

The analyses will be performed as described in V0.

Adverse events attributable to the treatment will be recorded.

Patients will be asked to stop the treatment.

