**Table 1: study schedule**

	V0	V3 months	V6 months
Inclusion/exclusion criteria	x		
Sign Informed consent	x		
Delivery of product	x		
Sociodemographic data	x		
Semen samples collection	x	x	x
Seminal analysis	x	x	x
Sperm DNA fragmentation	x	x	x*
Static Oxidation Reduction Potential	x	x	x
Sperm ROS intracellular and sperm DNA oxidation	x	x	x*
Hormones	x	x	x
Collection of excess product and empty blisters		x	
Adverse events**		x	x

\* If an improvement of this parameter is not obtained in V3, it will not be evaluated at this visit.

\*\* Adverse events will be collected from the first intake of the product and during the 6 months of the study.

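### Section 7.2 compares the arms visit by visit and never uses a man's baseline semen value: the test is valid, but it loses precision, leaves chance imbalance unadjusted and plans no effect estimate

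*Combined protocol and SAP*

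**What the plan says.** Section 7.2 gives the efficacy comparison in one sentence: "The non-parametric Mann-Whitney test will be applied to evaluate the effects of the dietary supplementation with TetraSOD® group vs. placebo group". By its closing words, the comparison is made visit by visit, that is, "at the same time of study (time 0, 90 d or 180 d"). The same test is run at time 0, and no change score is defined. It therefore acts on the values recorded at each visit. The word raw is not the protocol's, but no other reading fits.

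Two other planned analyses touch baseline, and neither adjusts the treatment contrast:

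- "Within each experimental group (TetraSOD® and placebo), the non-parametric Friedman test for matched-pairs will be applied" across the three sampling times. This is the only planned use of paired data, and it stays inside one arm.
- "Initial demographic and anthropometric characteristics of patients in TetraSOD® and placebo groups will be compared with independent t-test" or chi-square. No action follows from the result.

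The baseline values exist. Table 1 marks the row "Semen samples collection" at V0, V3 months and V6 months. Section 6.2 says: "During this visit semen samples will be collected as was done at V0". Section 6.1 lists seminal analysis, DNA fragmentation, sORP, intracellular ROS and DNA oxidation at V0.

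Section 5.1 admits "Male patients with idiopathic infertility classified with asthenozoospermia, oligozoospermia or oligoasthenozoospermia after seminal assessment". Section 4 describes block randomization at 1:1 and mentions no stratification by diagnosis or semen value.

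**The concern.** The main objective in section 3.1 is improvement after three months, which is a question about where each man started. The planned between-arm test does not know where he started.

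Entry mixes men with low concentration, low motility or both, so part of the spread at 90 d may already be present at V0. The documents give no figure for how much. Whatever that share is, an unadjusted test treats it as noise. If the arms differ by chance at V0, part of that difference passes into the 90-day contrast. The time-0 Mann-Whitney test could flag such a gap, but section 7.2 gives no step to follow, which leaves room for a choice made after seeing the data.

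Section 7.1 sizes the trial on a difference between means. Section 7.2 plans descriptive summaries and p-values, but no between-arm difference with a confidence interval.

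**Working it through.** **Inputs from the documents.** Section 7.1: difference 20, SD 25, drop-out 20%, 50 recruited per arm, and "accepting an alpha risk of 0.01 and a beta risk of 0.2 in a two sided test". Section 7.2: significance at p < 0.05. Completers per arm: 50 × 0.8 = 40.

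**Assumptions.** The baseline to 90-day correlation r is not given, so 0.3, 0.5 and 0.7 are shown. Baseline SD is taken as 25, data as normal, and the effect as a shift.

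**1. The plan's own figure.** n per arm = 2 × [25 × (2.576 + 0.842)/20]² = 36.5. Dividing by 0.8 gives 45.6, which rounds up to the stated 46. The calculation reproduces. It uses the unadjusted SD and no baseline information.

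**2. What adjustment does to the SD.** Residual SD = 25 × √(1 − r²). In precision, 40 men analysed with baseline are worth 40/(1 − r²) men analysed without it.

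| r | residual SD | equivalent n per arm | power at alpha 0.01, difference 20 (normal approximation) |
|---|---|---|---|
| unadjusted means | 25.0 | 40 | 0.84 |
| 0.3 | 23.8 | 44.0 | 0.88 |
| 0.5 | 21.7 | 53.3 | 0.94 |
| 0.7 | 17.9 | 78.4 | 0.99 |

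Power here is Φ(20/SE − 2.576) with SE = residual SD × √(2/40). For Mann-Whitney, with efficiency 3/π on normal data, the same formula gives about 0.82.

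**3. Simulated power, 40 per arm.** Repeated runs agree to about one or two percentage points.

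| effect and alpha | Mann-Whitney | ANCOVA, r = 0.3 / 0.5 / 0.7 |
|---|---|---|
| 0.8 SD (20/25), alpha 0.05 | 93% | 96 / 98 / 99.9% |
| 0.8 SD, alpha 0.01 | 79% | 86 / 93 / 99% |
| 0.5 SD (illustrative), alpha 0.05 | 57% | 63 / 72 / 86% |

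The first row pairs the section 7.1 effect with the section 7.2 threshold. The second uses the section 7.1 alpha. The 0.5 SD effect is not in the documents; it shows what happens if the true effect is smaller than planned.

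**4. Error rate.** With no true effect, Mann-Whitney rejects in 4.4% to 5.3% of simulated trials at nominal 5%, and ANCOVA in about 5%. Both are valid over randomizations.

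**5. Chance imbalance in the one trial run.** SE of the baseline difference = 25 × √(2/40) = 5.6. The 95% range is ±1.96 × 5.6 = ±11, over half the target of 20. An unadjusted comparison carries r times the gap forward: for a gap of 11, that is 3.3, 5.5 or 7.7. About 13% of null trials have a baseline gap beyond 1.5 SE. Among those, over 20,000 trials per setting, Mann-Whitney rejects at nominal 5% in about 8%, 12% and 19% at r = 0.3, 0.5 and 0.7, and ANCOVA in about 5%. Runs of 3,000 trials, with only about 400 qualifying trials each, gave up to 24% at r = 0.7.

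**6. Why not a simple change score.** Its SD is 25 × √(2(1 − r)), which is below 25 only if r exceeds 0.5. At r = 0.3 it is 29.6, and the required n rises from 37 to 52 per arm.

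**The case against.** The strongest defence is that the planned test is legitimate. Arms are randomized, Mann-Whitney tolerates skewed semen data, and its error rate is correct. That stands. A reader might infer from the imbalance figures that the trial is biased or its type I error inflated. The documents do not support this: the inflation appears only when one conditions on an unlucky baseline draw, and averages out over randomizations.

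A reader might also infer that the trial is underpowered. On the plan's own effect and analysis threshold, Mann-Whitney already has about 93% power, so adjustment adds roughly 3 to 7 points. The larger gaps need either the stricter alpha of section 7.1 or an effect smaller than the plan assumes. This also stands.

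The gain depends on r. Entry is restricted to men with low values, and those below 5 × 10⁶/ml are excluded, which could lower r. The low end therefore belongs in the range. At r = 0.3 the gain is modest but present in every setting simulated.

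The Friedman tests do not fill the gap. Significance in one arm and not in the other is not a comparison of arms. Nor does skewness defend the omission: in simulation on normal data, rank-based ANCOVA kept most of the gain (difference 10, alpha 0.05: 46%, 49% and 64%, against 40% to 42% for Mann-Whitney).

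Any remedy has limits. A log-scale ANCOVA estimates a ratio, not the mean difference in section 7.1, and a log scale is a doubtful default for percentages such as motility and vitality.

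**Conclusion.** The point holds as a matter of efficiency and reporting, and it should be changed. Section 7.2 leaves V0 out of the treatment comparison, so it gives up precision, leaves realised baseline imbalance unadjusted, and plans no between-arm estimate with an interval. It is not a validity failure, and it does not show inadequate power under the plan's inputs.

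The loss is about 3 to 7 percentage points of power for 0.8 SD at alpha 0.05, about 7 to 20 points at alpha 0.01, and about 6 to 29 points for an illustrative 0.5 SD at alpha 0.05, as r runs from 0.3 to 0.7. These figures rest on 40 completers per arm, normal data, equal SDs at both visits and an assumed r. Pilot data, if they include paired values, could narrow the range.

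**What to change.** Replace the between-arm sentence for 90 d in section 7.2 with wording to this effect: for each seminal parameter, the 90-day value will be compared between arms by ANCOVA, with arm and the V0 value of the same parameter as covariates, and the adjusted difference (or ratio, if log-transformed) will be reported with a 95% confidence interval.

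- Fix the scale for each parameter before unblinding: raw or transformed for counts, untransformed or rank-based for percentages. The raw scale is the one that estimates the mean difference in section 7.1. A rank-based analysis gives no difference in natural units, so report the untransformed adjusted difference beside it.
- Keep the 90-day Mann-Whitney test as a sensitivity analysis.
- Drop the time-0 outcome tests and describe baseline by arm instead.
- Entry diagnosis as a further covariate is optional. It is not a stated stratification factor, and its benefit was not assessed here.

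Section 3.3 names all WHO seminal parameters as main variables, so which of these models is primary depends on a choice the protocol has yet to make.

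The cost is a paragraph of analysis text and possibly a statistics package beyond Prism 6. No new patients, visits or assays are needed.

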## 5 Selection of participants

Adult asthenozoospermic, oligozoospermic or oligoasthenozoospermic males who come to the Uroandrology unit of “Hospital Clínic de Barcelona” of Barcelona.

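### Change over time is tested only within each arm by Friedman tests; the between-arm test is valid but ignores baseline, and no test is named as primary

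*Combined protocol and SAP*

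**What the plan says.** Section 7.2 of the combined protocol and SAP plans two kinds of efficacy test.

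- **Between arms:** "The non-parametric Mann-Whitney test will be applied to evaluate the effects of the dietary supplementation with TetraSOD® group vs. placebo group", at each of 0, 90 and 180 days.
- **Within each arm:** "the non-parametric Friedman test for matched-pairs will be applied in order to determine statistically significant differences of data recorded at the three sampling times".

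One threshold covers both: "Significance will be accepted for" p < 0.05. The section names no primary test, no between-arm comparison of change, no baseline adjustment and no handling of missed visits.

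Other sections bear on this:

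- The main objective (3.1) is improvement after 3 months. The main variable (3.3) is the whole set of WHO semen parameters.
- The 180-day visit follows a 3-month wash-out (section 4).
- Participants are "Adult asthenozoospermic, oligozoospermic or oligoasthenozoospermic males" (section 5). Eligibility is confirmed at V0, where the baseline semen sample is also taken (6.1). Whether that sample is the one that qualifies the man is not stated.
- At 6 months, DNA fragmentation and ROS/DNA oxidation are not measured if they did not improve at 3 months (6.3, Table 1).
- The sample size (7.1) targets a between-arm difference, "With the aim to determine differences between the mean of the two experimental groups", "with an anticipated drop-out rate of 20" per cent.

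**The concern.** The objectives are about improvement, and the only analysis of improvement is done inside each arm. A Friedman test in the TetraSOD arm asks whether values differ across three visits. It does not ask whether they changed more than on placebo. It is also an omnibus test whose third time point is off treatment, so a significant result does not isolate 0 versus 90 days.

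Both kinds of test carry the same threshold and neither is primary. Nothing in the plan therefore stops a report from resting on a significant result on TetraSOD and a non-significant one on placebo.

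Two features add to this. Men enter because a semen value is low, so if the baseline sample is the qualifying one, values tend to rise on re-measurement in both arms. And the Friedman test uses only men with all three values, although the main objective needs only the first two visits.

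The between-arm test avoids these faults but leaves the baseline values unused, at a cost in precision.

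**Working it through.** **1. The plan's own figure.** Inputs from 7.1: difference 20, SD 25, two-sided alpha 0.01, power 0.80, drop-out 20%.

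n per arm = 2 × [25 × (2.576 + 0.842) / 20]² = 36.5, so 37 evaluable men. Allowing for drop-out, 36.5 / 0.8 = 45.6, so 46. The stated 46 is reproduced.

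**2. Discordant Friedman results without regression to the mean.** If each test has size 0.05 and the arms are independent:

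- TetraSOD significant and placebo not: 0.05 × 0.95 = 4.75%.
- Exactly one arm significant: 2 × 4.75% = 9.5%.

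Simulation with a separate qualifying sample (40 or 50 per arm) agrees: each Friedman test rejects in 4.2-5.3% of trials, TetraSOD alone is significant in about 4-5%, and one arm only in about 8-11%. If both arms truly change by the same amount (0.3-0.5 SD of the within-man difference, 40 per arm, correlation 0.7), one arm only is significant in 37-51% of trials.

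**3. Regression to the mean, if the V0 sample qualifies the man.** Assumptions not in the documents: normal scale, no treatment effect, 40 men per arm, test-retest correlation 0.5-0.9, entry cut at the median or 1 SD below the mean.

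| Entry rule | Null rejection, one Friedman test |
|---|---|
| Low on the tested variable | about 14-100% |
| Low on either of two variables correlated 0.4 | about 7-78% |

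As an example, with entry below the median on the tested variable, rejection is 65.5%, 40.6% and 15.9% at correlations 0.5, 0.7 and 0.9. TetraSOD alone is significant in about 0-26% of trials across these settings. That share is p(1 − p), where p is the rejection rate. It peaks at 25% when p = 0.5 (26% is simulation noise) and falls towards 0 when both arms nearly always reject.

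**4. The between-arm test under the same selection.** The 90-day Mann-Whitney test rejects in 4.3-5.3% of null trials in every setting of the 40- and 50-per-arm runs. Selection affects both arms alike, so the comparison keeps its size.

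**5. Complete blocks.** With an assumed 5%, 10% or 20% missing independently at each of V3 and V6:

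| Missing per visit | In Friedman, of 50 | In 90-day Mann-Whitney, of 50 |
|---|---|---|
| 5% | 50 × 0.95² = 45.1 | 47.5 |
| 10% | 50 × 0.90² = 40.5 | 45 |
| 20% | 50 × 0.80² = 32 | 40 |

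For DNA fragmentation and ROS/DNA oxidation, the V6 rule adds a further limit. Applied per man, only improvers have three values. Applied per group, a parameter that did not improve has no three-time test.

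**6. What baseline adjustment needs.** n = 36.5 × (1 − r²), where r is the assumed correlation between baseline and 90 days:

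- r = 0.5: 36.5 × 0.75 = 27.4
- r = 0.7: 36.5 × 0.51 = 18.6
- r = 0.9: 36.5 × 0.19 = 6.9

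With 20% drop-out from 50, 40 men per arm are evaluable, which exceeds all three.

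**The case against.** The strongest reply is that the plan already has a valid efficacy test. Section 7.2 assigns the effect of supplementation to the Mann-Whitney test and gives the Friedman test only the differences between sampling times. The sample size rests on a between-arm difference as well. This stands, and it rules out three stronger readings that a reader might infer:

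- That the trial has no valid test of treatment. It does, and regression to the mean does not bias that test.
- That persistence after stopping is untested. The 180-day Mann-Whitney test compares the arms at the end of wash-out, though without baseline adjustment.
- That 90-day data are thrown away. A man with no 180-day sample leaves the Friedman test but stays in the 90-day Mann-Whitney test.

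A second reply is that regression to the mean is not established. This also stands: sections 5.1 and 6.1 do not say whether V0 supplies the qualifying sample, and a separate one returns the Friedman test to about 5%. Its size is uncertain too. Entry is on low concentration or low motility, and section 5.2 excludes concentrations below 5 × 10⁶/ml. With entry on either of two variables and an assumed lower cut at −1.5 or −2 SD, null rejection at correlations 0.5-0.7 is 8-12% (median cut) or 38-68% (1 SD cut), and 6-18% at correlation 0.9. COMET, sORP and ROS are not entry criteria, so they are affected only through correlation.

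Neither reply supplies a between-arm analysis of change, a baseline adjustment or a named primary test.

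**Conclusion.** The concern holds in a limited form. The plan's arm comparison is valid but unadjusted. Its only analysis of change cannot test TetraSOD against placebo, yet it carries equal standing at p < 0.05.

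The weakness in comparing the two Friedman results does not depend on regression to the mean: one arm alone is significant in about 8-11% of null trials, and in 37-51% when both arms change equally under the assumed settings. Regression to the mean could make it worse, with null rejection anywhere from about 7% to 100%. That range rests on assumed correlations and cut-offs, and on V0 being the qualifying sample. It should be read as an exposure, not as a demonstrated bias.

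The loss of incomplete men applies to the Friedman test only. Its size depends on when drop-out occurs, which the documents do not say.

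This should be changed before the data are analysed. It does not invalidate the design or call for more men.

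**What to change.** Amend section 7.2 as follows.

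1. Report within-arm change descriptively, without inferential p-values.
2. Name one efficacy test: a baseline-adjusted between-arm comparison at 90 days, in all randomised men with post-baseline data. ANCOVA would serve, or a mixed model with arm, visit, arm-by-visit and baseline.
3. Use the baseline-adjusted 180-day arm contrast for persistence after stopping.
4. Choose the scale by outcome, for example log for counts. Do not apply it automatically to percentages such as motility or vitality, where zeros can occur.
5. State how missed visits are handled and whether the V0 sample determines eligibility.
6. State whether the V6 rule for DNA fragmentation and ROS/DNA oxidation works per man or per group. If it works per man, the 180-day contrast for those outcomes includes improvers only and should not be read as a randomised comparison.

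Separately, the efficacy test needs one significance level: 7.1 plans "accepting an alpha risk of 0.01 and a beta risk of 0.2 in a two sided test", while 7.2 uses 0.05.

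The cost is SAP wording, a little more analysis work, possibly in software other than the named Prism 6, and the loss of within-arm p-values. No extra men or visits are needed.
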